9.2.2. Exclusion of Data from Analysis

No data will be excluded from any analysis.

9.2.3. Criteria for Evaluation

The primary evaluation will be to assess the cutaneous irritation and sensitisation potential of the test and control product, based on the irritation (dermal response) and superficial irritation (other effects) score/grade after patch removal during the induction and challenge phase using the ITT population.

Safety and tolerability will be evaluated by adverse events assessments using the Safety population.

9.2.4. Handling of Dropouts and Missing Data

Missing data will not be replaced or imputed. Dropouts will be included in analyses up to the point of discontinuation.

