2. OBJECTIVE(S) AND ENDPOINT(S)

| Objective(s) | Endpoint(s) |
|--|--|
| Primary | |
| To determine the irritation and contact | Trained assessor assessment of local |
| sensitisation potential of a cosmetic facial | tolerance through visual assessment of |
| skin product after repeated patch | cutaneous irritation via the combined |
| applications to the skin of healthy | dermal response and other effects scores |
| subjects. | over the induction and challenge phase. |
| Secondary | |
| To evaluate the general safety of a | Assessment of frequency and severity of |
| cosmetic facial skin product. | Adverse Events |

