Any skin response at a patched site will be clinically assessed using the criteria recommended by the US Department of health and Human Services Food and Drug Administration (FDA), 1999.

Each of the scores represents an effect that is localised in a representative portion of the patch area, defined as 25% or more of the patch test site. Individual observations will be recorded in tables and a narrative description of all skin responses (any

| Document Name | Gsikni2θ/1965t-prot/207 1585 | | | |
|----------------------|---------------------------------------|---------------------|----------------------|--|
| Туре | Version | Document Identifier | Effective Date | |
| eldo climitralleatoc | 0.0; CURRENT; Most-Recent; Registived | 090032d580e42556 | 31-Jan-2017 14:20:06 | |
| Reason For Issue | Auto Issue | | | |

score>0) will be provided. Superficial irritation scores are only provided if there is a dermal response score >0.

Each Superficial Irritation Score should be reported as a letter. The combined score will equal the sum of the dermal response score plus the numerical equivalent of the superficial irritation score (e.g. dermal response score=3 and superficial irritation score=" $^{\circ}$ C" implies a combined score of 3 + 2 = 5).

If a subject develops a combined score of 3 or greater at any point during the Induction phase, the patch will be applied to an adjacent naïve site for the next application. If a combined score of 3 or greater occurs at the naïve site, no further patch applications will be made. Such reactive subjects will however, receive patches on naïve test sites during the challenge phase of the study unless, in the opinion of the Investigator, it would be unwise to do so.

Dermal irritation or sensitisation reactions within the patch area (i.e., irritation reactions outlined in Appendix 2) will not be recorded as AEs during the study. Reactions to the patch itself will also not be recorded as AEs. Unexpected reactions (e.g., rash, hives) will be recorded as AEs. These responses are expected in these study conditions and will be disregarded in evaluations, using the negative control (saline solution) as the standard for determining the expected degree of reaction.

Application Amount Justification:

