5.2. Application Schedule

Induction Phase:

Visit 2/Day 1 of the induction phase could be combined with Visit 1.

On Day 1 of the Induction Phase, eligible subjects will return to the study site and another dermatological assessment will be conducted to ensure subject continued eligibility (if Visits 1 and 2 are not combined), as well as a review of concomitant medications since screening. The test site will be designated above the waist between the left scapula and waistline and away from the spinal mid-line. The site of application of the products will then be randomly assigned. Baseline grading/assessment of the test sites will then be performed.

There will be 9 patch applications to the same test site with the test product and saline solution over 3 consecutive weeks during the Induction phase, with patches applied on alternate weekdays each week (Monday, Wednesday, and Friday). Each patch will remain in place for $48 (\pm 2)$ hours on weekdays and $72 (\pm 2)$ hours on weekends. The patches will be removed and the treated areas will be cleaned with saline solution. After 30 minutes (maximum of 1 hour) the site will be graded/evaluated, new patches will be applied to the same site.

If a subject develops a combined score of 3 or greater at any point during the Induction phase, the patch will be applied to an adjacent naïve site for the next application. If a combined score of 3 or greater occurs at the naïve site, no further patch applications will be made. Such reactive subjects will however, receive patches on naïve test sites during the challenge phase of the study unless, in the opinion of the Investigator, it would be unwise to do so.

Rest Phase:

After the last patch removal and grading/evaluation of the Induction Phase, subjects will enter a Rest Phase of 2 weeks. During this time there will be no patch applications.

| Document Name | G\$in:i2:071985t-prot@207 585 | | |
|----------------------|--|---------------------|----------------------|
| Туре | Version | Document Identifier | Effective Date |
| eldo climitralleatbo | 0.0; CURRENT; Most-Recent; Rfferitived | 090032d580e4@556 | 31-Jan-2017 14:20:06 |
| Reason For Issue | Auto Issue | | |

Challenge Phase:

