2.4.2 Handling of missing values/censoring/discontinuations

Missing data will not be replaced or imputed. Dropouts will be included in analyses up to the point of discontinuation.

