Protocol: 207585

Program Run Date:ddmonyyyy

Table 14.2.1.1
Frequency of Combined Score by Phase, Visit and Treatment and Maximum Combined Score
Intent to Treat Population

Intent to Treat Population (N=XX)

Phase: Induction Phase

Visit	Combined Scores	Facial micellar cleanser		Saline Solution	
		(N=XX)	n	(N=XX)	n
Subjects with at least one combined score > 0 at any visit n (%)		xx (xx.x)		xx (xx.x)	
Subjects with no combined score > 0 at any visit n (%)		xx (xx.x)		xx (xx.x)	
VISIT 2	0	xx		xx	
	1	xx		xx	
	2	xx		xx	
	3	xx		xx	
	4	xx		xx	
	5	xx		xx	
	6	xx		xx	
	7	xx		xx	
VISIT 3		xx		xx	
		xx		xx	
		xx		xx	
VISIT 10		xx		xx	
		xx		xx	
MAXIMUM COMBINED SCORE	1	xx		xx	
	2	xx		xx	
	3	xx		xx	
	4	xx		xx	
	5	xx		xx	
	6	xx		xx	
	7	xx		xx	

Combined Score: Dermal response Score + Superficial response score (>0)

Page x of y

PPD

Programming Note:

- Induction Phase include visit 2 till visit 10.
- Rest Phase include Visit 11
- Challenge Phase include visit 12 till visit 15
- This table is only required if at least one subject reports a combined score >0
- Maximum combined Score will be calculated and displayed at the end of each phase irrespective of visits.

Document Name	gsk-207585-reporting-and-analysis-plan		
Type	Version	Document Identifier	Effective Date
eldo_controlled	0.1; CURRENT; Most-Recent; Reviewed	090032d580e125d0	
Reason For Issue			

Protocol: 207585

Program Run Date:ddmonyyyy

Table 14.2.2.1
Frequency of Dermal Response Score by Phase, Visit and Treatment and Maximum Dermal Response Score
Intent to Treat Population

Intent to Treat Population (N=XX)

Phase: Induction Phase

Visit	Score	Facial micellar cleanser	Saline Solution
		(N=XX)	(N=XX)
		n	n
Subjects with at least one dermal response score > 0 at any visit n (%)		xx (xx.x)	xx (xx.x)
Subjects with no dermal response score > 0 at any visit n (%)		xx (xx.x)	xx (xx.x)
VISIT 2			
0		xx	xx
1		xx	xx
2		xx	xx
3		xx	xx
4		xx	xx
5		xx	xx
6		xx	xx
7		xx	xx
VISIT 3			
VISIT 4			
.....			
VISIT 10			
MAXIMUM DERMAL RESPONSE SCORE		xx	xx
.....			

0 = No evidence of irritation; 1= Minimal erythema barely perceptible; 2 = Definite erythema; readily visible;or minimal edema; minimal popular response; 3 = Erythema and papules;4 = Definite edema; 5 = Erythema, edema and papules; 6 = Vesicular eruption; 7 = Strong reaction spreading beyond test site

Page x of y

Programming Note:

- Induction Phase include visit 2 till visit 10.
- Rest Phase include visit 11
- Repeat for the challenge phase.

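### Induction reactors left unchallenged at the investigator's discretion have no challenge reading and can be tabulated as challenge-phase non-responders

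*Protocol*

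**What the plan says.** Protocol 5.2 sets out what happens to reactors, and 3.4, 6.2.2 and Appendix 2 repeat it. The first step applies "If a subject develops a combined score of 3 or greater at any point during the Induction phase": the next patch goes to an adjacent naïve site. Then: "If a combined score of 3 or greater occurs at the naïve site, no further patch applications will be made". The default at challenge is that "Such reactive subjects will however, receive patches on naïve test sites during the challenge phase of the study", with the exception "unless, in the opinion of the Investigator, it would be unwise to do so". No criteria for the exception and no expected number are given.

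The only missing-data rule is in Protocol 9.2.4, "Missing data will not be replaced or imputed. Dropouts will be included in analyses up to the point of discontinuation", repeated in SAP 2.4.2 ("Missing data will not be replaced or imputed"). SAP 2.4.1.3 plans no supportive analysis.

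Under SAP 2.1.3 the ITT population needs randomisation and a score from at least one test site, so an unchallenged reactor stays in it. The shell of Table 14.2.1.1 (SAP 5.1) uses the ITT N as column header. Above the visit-by-visit counts it has two rows: subjects with at least one combined score above zero, and "Subjects with no combined score > 0 at any visit n". Its programming note defines the challenge phase as Visits 12 to 15. Protocol Schedule of Events, note h, places the Visit 12 grading before the challenge patch is applied.

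**The concern.** A challenge reading skipped under this clause is not missing at random. It is missing because the subject reacted during induction, and it is a reading on the very response that the challenge phase is there to measure. Nothing in either document counts these subjects, flags them in the challenge table, or tests what they could do to the result.

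The table shell makes this worse. It has no row for subjects not challenged, and its challenge phase opens with a reading taken before any challenge exposure. Followed literally, it lets a subject who was never challenged be shown as having been challenged without reaction.

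Other outputs give little protection. Reactions gradable under Appendix 2 are generally not adverse events (Protocol 7.1.1). The discontinuation reasons in Protocol 6.3.1 include no patch-reaction category. The list of listings in SAP 4.3 contains no listing of individual dermal scores. At stake is a challenge-phase frequency that looks cleaner than the data support, in a study whose primary objective includes contact sensitisation.

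**Working it through.** **Inputs.** 200 evaluable completers, at least 240 randomised, and the statement that no reaction in 200 gives 95% certainty of a rate below 1.8% (Protocol 3.3 and 9.1; SAP 2.8). The number *m* of reactors left unchallenged is not in the documents; the values below are assumptions.

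**Step 1: the plan's own figure.** With 0 events in *n*, the exact (Clopper-Pearson) two-sided 95% upper limit is 1 − 0.025^(1/*n*). For *n* = 200 this is 1.83%, which matches the stated 1.8%. The one-sided version, 1 − 0.05^(1/200), is 1.49%, so the plan's figure is the two-sided one.

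**Step 2: how one subject passes through the table.** Take a reactor who attends Visit 12, is graded 0 on naïve skin, and is not patched.
- The subject is in the ITT N, having induction scores.
- The only challenge-phase score is the 0 at Visit 12; Visits 13 to 15 are blank and not imputed.
- The subject has no challenge-phase score above zero, so of the two rows only the second fits.

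If the subject has no Visit 12 grading either, the shell does not say where the subject goes, but the N in the header still includes them.

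**Step 3: direction.** Let *k* be the observed challenge responders, *N* all subjects, and *q* the unknown share of the *m* skipped reactors who would have responded.
- ITT denominator: the table shows *k*/*N* against (*k* + *mq*)/*N*. The shown value is never the larger.
- Challenged-only denominator: *k*/(*N* − *m*) is too low only if *q* exceeds *k*/(*N* − *m*).

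Example with *k* = 2, *N* = 200, *m* = 5: shown 2/200 = 1.00% or 2/195 = 1.03%. With *q* = 0.5 the full figure is (2 + 2.5)/200 = 2.25%; with *q* = 1 it is 7/200 = 3.50%.

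**Step 4: size of the extreme case.** Assume no challenged subject reacts, and count every skipped reactor as a responder (*q* = 1). The upper limit for *x*/*n* is the 0.975 quantile of Beta(*x* + 1, *n* − *x*).

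| *m* | Observed only, 200 in all (upper limit) | Counted as responders, 200 in all | Counted as responders, 240 in all |
|---|---|---|---|
| 1 | 0/199 (1.84%) | 1/200 = 0.50% (2.75%) | 1/240 = 0.42% (2.30%) |
| 3 | 0/197 (1.86%) | 3/200 = 1.50% (4.32%) | 3/240 = 1.25% (3.61%) |
| 5 | 0/195 (1.87%) | 5/200 = 2.50% (5.74%) | 5/240 = 2.08% (4.79%) |

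The observed-only column hardly moves with *m*. Correcting the denominator alone therefore does not show what the skipped subjects could change.

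**The case against.** The strongest reply is that nothing the plan formally estimates is biased. A reader might infer that these subjects vanish from the results, that they can never count as reactors, and that a sensitisation rate is driven toward zero. The documents do not support that. Neither document defines a sensitisation case or rate. The primary endpoint uses the combined "dermal response and other effects scores" over both phases. An unchallenged reactor is counted in the induction frequencies and the induction maximum, and Protocol 9.3.2 promises a narrative of every skin response. Only the challenge reading is absent.

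A reader might also infer that the 1.8% statement fails once one reactor is skipped. That does not follow either. It is a design-stage statement, the analysis plans no formal inference, and its word for a reaction is not limited to challenge. If induction reactions count, a skipped subject has already broken its zero-reaction condition.

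The default is to challenge reactors, so the exceptions may be few or none. A combined score of 3 or more may be irritation rather than sensitisation, so counting every skipped reactor as positive may overstate the response. Finally, treating an unread site as zero would itself be an imputation, which the plan rules out.

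All of this stands except the last point, which holds only in part. The Visit 12 zero is a recorded score, not an imputed one, so the no-imputation rule does not prevent the misplacement. The other points limit how far the concern reaches; they do not supply the missing row or the missing denominator.

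**Conclusion.** The point holds for the challenge-phase tabulation. A subject not challenged because of an induction reaction can be shown as a challenge-phase non-responder, and with the ITT denominator the resulting error can only lower the challenge-phase response frequency. With a challenged-only denominator it lowers it only if skipped reactors would have responded more often than those challenged, which is plausible but is an assumption.

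The size depends on a number the documents do not give. With no other reaction, one such subject separates an upper limit of 1.84% (0/199) from 2.75% (1/200), or 2.30% on 240. These figures take every skipped reactor as a responder and so are a conservative bound, not an estimate. If nobody is skipped, there is no effect. For the same reason the conservative count should stand beside the observed result and not replace it as the basis of the conclusion.

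**What to change.** In SAP 2.4.2 and the challenge block of Table 14.2.1.1:

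1. For each product, use as denominator the subjects who received the challenge patch and have at least one reading after its removal (Visits 13 to 15). Show Visit 12 separately as a pre-patch baseline, outside the challenge response and the challenge maximum.
2. Add a row for subjects not challenged, or withdrawn before challenge, because of an induction reaction. This requires the reason for non-challenge to be recorded.
3. Add a sensitivity tabulation that counts those subjects as challenge responders for the product that reacted. Label it a conservative bound, and state whether any no-reaction conclusion still holds under it.

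The cost is SAP wording, one extra row and one extra count. The downside is a possibly less favourable bound, since some of these reactions may be irritation; this arises only if such subjects exist. The clinical decision whether to challenge is unchanged.

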9.3. Statistical Methods and Analytical Plan

Additional details of the proposed statistical analysis will be documented in the statistical analysis plan (SAP), which will be written following finalization of the protocol and prior to study unblinding.

| Document Name | @sikvi20179@sitqurot@07 1585 | | |
|-----------------------|---------------------------------------|---------------------|----------------------|
| Туре | Version | Document Identifier | Effective Date |
| eldo climitarelleatoc | 0.0; CURRENT; Most-Recent; Revietived | 090032d580e42d66 | 31-Jan-2017 14:20:06 |
| Reason For Issue | Auto Issue | | |

9.3.1. Demographic and Baseline Characteristics

Age will be summarized using descriptive statistics such as means, medians and standard deviations. Gender, race and Fitzpatrick skin type will be summarized using frequency counts and percentages.

9.3.2. Primary Analysis(es)

The primary analysis will be based on the irritation (dermal response) and superficial irritation (other effects) scores/grades assessed using the scales described in Tables 1 and 2 of Appendix 2. Individual observations will be assessed based on these scales and a narrative description of all skin responses, both in the induction and challenge phases, will be provided.

No formal statistical inference will be performed.

The number and percentage of subjects recording each category of score/grade, as well as any skin response versus those without any skin response will be presented by treatment group at each assessment time point and over the induction and challenge phases using the maximum grade/score. If there are subjects with non-zero dermal response or other effects scores, then the dermal response, other effects and a combined dermal and others effects score will be summarised using descriptive statistics at each assessment time point and over the induction and challenges phases using a total score across time points.

9.3.3. Safety Analysis(es)

Adverse Events (AE) will be tabulated according to the current version of the MedDRA. Frequencies and percentages will be presented overall, for each system organ class, and for each preferred term. Summaries of treatment-emergent AEs, treatment-related AEs, AEs leading to discontinuation, and serious AEs will be completed. For treatment-related or treatment skin site related AEs, these will also be presented by product/test site.

10. STUDY GOVERNANCE CONSIDERATIONS

10.1. Posting of Information on Publicly Available Clinical Trials Registers

Study information from this protocol will be posted on publicly available clinical trial registers before enrollment of subjects begins.

| Document Name | G\$in:i2:071985teparot@00 1585 | | |
|-----------------------|---|---------------------|----------------------|
| Туре | Version | Document Identifier | Effective Date |
| eldo climitarelleatoc | 0.0; CURRENT; Most-Recent; Rfferietiwed | 090032d580e4@556 | 31-Jan-2017 14:20:06 |
| Reason For Issue | Auto Issue | | |

10.2. Regulatory and Ethical Considerations, Including the Informed Consent

The study will be conducted in accordance with all applicable regulatory requirements, and with GSK policy.

The study will also be conducted in accordance with ICH Good Clinical Practice (GCP), all applicable subject privacy requirements, and the guiding principles of the current version of the Declaration of Helsinki. This includes, but is not limited to, the following:

- 1. Before initiating a trial, the investigator/institution should have written and dated approval/favorable opinion from the IRB for the trial protocol (including amendments), written informed consent form, consent form updates, subject recruitment procedures (e.g., advertisements), investigator brochure/ safety statement (including any updates) and any other written information to be provided to subjects. A letter or certificate of approval will be sent by the investigator to the sponsor prior to initiation of the study, and also when subsequent amendments to the protocol are made.
- 2. Signed informed consent to be obtained for each subject before participation in the study (and for amendments as applicable).
- 3. Investigator reporting requirements (e.g. reporting of AEs/SAEs/protocol deviations to IRB).
- 4. GSK will provide full details of the above procedures, either verbally, in writing, or both.

10.3. Quality Control (Study Monitoring)

In accordance with applicable regulations including GCP, and GSK procedures, GSK or designee (i.e. third party vendor) monitors will contact the site prior to the start of the study to review with the site staff the protocol, study requirements, and their responsibilities to satisfy regulatory, ethical, and GSK requirements.

When reviewing data collection procedures, the discussion will include identification, agreement and documentation of data items for which the CRF will serve as the source document.

| Document Name | G\$iki2871985tqprot2007 1585 | | |
|----------------------|---------------------------------------|---------------------|----------------------|
| Туре | Version | Document Identifier | Effective Date |
| eldo climitralleatoc | 0.0; CURRENT; Most-Recent; Registived | 090032d580e42556 | 31-Jan-2017 14:20:06 |
| Reason For Issue | Auto Issue | | |

GSK or designee will monitor the study and site activity to verify that the:

- 1. Data are authentic, accurate, and complete.
- 2. Safety and rights of subjects are being protected.
- Study is conducted in accordance with the currently approved protocol and any other study agreements, GCP, and all applicable regulatory requirements.

The extent and nature of monitoring will be described in a written monitoring plan on file at GSKCH. The investigator (or designee) agrees to allow the monitor direct access to all relevant documents and agrees to co-operate with the monitor to ensure that any problems detected in the course of these monitoring visits are resolved.

10.4. Quality Assurance

To ensure compliance with GCP and all applicable regulatory requirements, GSK may conduct a quality assurance assessment and/or audit of the site records, and the regulatory agencies may conduct a regulatory inspection at any time during or after completion of the study.

In the event of an assessment, audit or inspection, the investigator (and institution) must agree to grant the advisor(s), auditor(s) and inspector(s) direct access to all relevant documents and to allocate their time and the time of their staff to discuss the conduct of the study, any findings/relevant issues and to implement any corrective and/or preventative actions to address any findings/issues identified.

The sponsor will be available to help investigators prepare for an inspection.

